9.2. STATISTICAL ANALYSIS OF EFFECTIVENESS

The main analyses will be conducted on the intention-to-treat sample. Clinical effects of treatment will be evaluated using mixed-model repeated-measures analyses where the pre-post comparisons of all outcome measures will include time as a within-group variable and the condition as a between-group variable. An incremental cost-effectiveness ratio (ICER) will be calculated to obtain the additional costs of iCBT-I in comparison with control condition. Cohen's d will be reported for all within-between comparisons based on estimated means and the pooled standard deviation from the observed means at pre- and posttreatment. To test significance of the difference between the number of responders in each treatment condition, we will use χ^2 -test. Regression analyses will be used to identify predictors of treatment outcome. We will test models using Akaike/Bayesian Information Criteria to select an optimal model with predictors of treatment outcome.

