3. STUDY DESIGN

- a) The proposed study is a multicenter parallel-group add-on superiority RCT comparing an active treatment condition (iCBT-I plus CAU) to CAU alone.

After signing the IC form, participants will receive an e-mail with the link to the Qualtrics Survey Software (Qualtrics, Provo, UT, USA), where they complete baseline assessment and receive the individual allocation code. On completion of baseline measures, subjects will be automatically assigned by the randomization function of Qualtrics Survey Software to either iCBT-I plus CAU or CAU group using single block randomization. Neither participants nor referring specialist nor the research team have foreknowledge and/or control over randomization and the allocation procedure. Following randomization, the participants will receive an automated email regarding their group allocation and a description of future steps. In case they were allocated to the treatment group, their individual code will provide an access to the iCBT-I program.

Participants in the control group will get access to the iCBT-I program after the 5-month follow-up (3 months after post-assessment) provided they completed the follow-up assessment and still fulfill eligibility criteria. In this group, an additional assessment will be conducted eight weeks after providing access to the CBT-I program to enlarge the sample for the analysis of outcome predictors.

The research team, except the trial coordinator, will be blind to allocation. Coding allocation form, along with the participant's real name and address noted in the IC form, will be stored in the password-protected computer of the trial coordinator. Participants will not be blind to treatment allocation and will receive information about their randomization outcome via email. Questionnaires and sleep diaries will be completed entirely online under the participant's individual code.

3.1.OUTCOMES

3.1.1. The primary endpoint of the present study is the change of Insomnia Severity Index (ISI) from pre- to post-treatment and at follow-up.

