4.1. CONCURRENT THERAPY

Both groups will have access to CAU. Interventions that are part of CAU may be assigned within the first visit to a referring doctor or at any point of the study on a next doctor visit. All concurrently applied treatments will be assessed repeatedly by self-report.

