9. STATISTICAL ANALYSIS

9.1. SAMPLE SIZE CALCULATION

We aim to detect a small to medium between-group effect size (Cohen's d) of 0.35 at post-treatment. The chosen effect size is reasonable since CAU being an active alternative treatment may decrease between-group outcome differences and a smaller effect size was considered to be irrelevant from a clinical point of view. Based on a-level of .05 and a power of .95 using a single-level repeated measures ANOVA power analysis with G*Power, the sample size needed is approximately 55 participants per group and 110 for the total sample. Our secondary aim is to find outcome predictors within participants who complete iCBT-I. In order to enlarge this sample, participants from the CAU group will get access to the iCBT-I program after the follow-up period.

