16. TIMEFRAMES OF THE STUDY

- Study approval at a Chair of neurology of Sechenov University meeting 26.11.2019
- Study approval by local ethical committee – February 2020
- Experimental part of the study – February 2020 – December 2021:

-
- Start of data collection – February 2020;
 - Inclusion of two additional clinical centres - February 2021;
 - Completion of data collection - December 2021;
 - Statistical analysis, publication of results – January-February 2022

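### The multicentre plan names neither a stratification factor nor a centre term; the analysis remains valid, and prespecifying centre and centre-by-time in the ISI model would be a cheap gain in precision.

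*Combined protocol and SAP*

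**What the plan says.** - **Design.** Section 3 calls the study a "multicenter parallel-group add-on superiority RCT". Participants are assigned by the survey software "using single block randomization". No stratification factor is named, and the block term is not defined further.
- **Centres.** Section 16 dates the start of data collection to February 2020, then lists "Inclusion of two additional clinical centres - February 2021", with completion in December 2021. The number of centres at the start is not given, nor are patients per centre.
- **Usual care.** Both arms receive it. Section 4.1 states: "Interventions that are part of CAU may be assigned within the first visit to a referring doctor". It may also be assigned at later visits. Section 4.2.1 sets no restriction on concurrent therapy, and section 9.1 treats CAU as an active alternative.
- **Analysis.** The mixed model in section 9.2 "will include time as a within-group variable and the condition as a between-group variable". Section 9.1 sizes the trial with a "single-level repeated measures ANOVA power analysis with G*Power". The available text has no centre covariate, random centre effect or analysis by centre.

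**The concern.** Without stratification, the arms can differ by chance in how many patients come from each centre. Usual care is active, unrestricted and set by the referring doctor, and two centres enter a year after the first patients, so centres could plausibly differ in how much ISI improves. A model with time and condition only leaves that variation in the error term. What is at stake is a little precision in the primary comparison, and whether any adjustment for centre is fixed in advance or chosen after the results are known.

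**Working it through.** **Inputs from the plan:** 55 per arm, 110 in total, d = 0.35, alpha 0.05, power 0.95 (section 9.1).

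**Assumed, because the plan gives no figure:** pre-post correlation rho = 0.5; centre shares of 20 to 50%; centre gaps in ISI change of 0.3 to 0.6 SD; three centres in the simulations.

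**1. The plan's own figure.** For the within-between interaction with f = d/2 = 0.175, m = 2 times and rho = 0.5, lambda = f² × N × m / (1 − rho) = 0.030625 × 110 × 2 / 0.5 = 13.475. This gives power 0.953, so N = 110 reproduces. It contains no allowance for centre. The same rho is used below.

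**2. Baseline precision.** The SD of change is √[2(1 − 0.5)] = 1 ISI SD. The SE of the difference in change is √(2/55) = 0.191, and the 95% half-width is 1.96 × 0.191 = 0.374 SD.

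**3. Chance imbalance.** Drawing 55 from 110, the SD of the between-arm difference in a centre's share p is 2√[p(1 − p)/109]:
- p = 0.20: 0.077
- p = 0.33: 0.090
- p = 0.50: 0.096

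In simulations with centre sizes from 90/10/10 to 37/37/36, the first centre's share differed between arms by at least 10 points in about 22 to 34% of randomisations, and by at least 20 points in about 1 to 4%.

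**4. Shift in the estimate** (SD of share difference × centre gap):
- Smallest: 0.077 × 0.3 = 0.023 SD; 95% limit 1.96 × 0.023 = 0.045.
- Largest: 0.096 × 0.6 = 0.058 SD; 95% limit about 0.11.

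**5. Effect on the interval.** The shift is one component of the sampling error, so it adds in quadrature:
- Smallest: √[1 + (0.045/0.374)²] = 1.007, or 0.7% wider.
- Largest: √[1 + (0.113/0.374)²] = 1.044, or 4.4% wider.

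**6. Cost of the term.** With three centres there are two extra parameters. The expected inflation of the SE is about 1/√(1 − 2/109) = 1.009, or 0.9%. Net of this, omitting centre widens the interval by between 1.007/1.009 − 1, about 0%, and 1.044/1.009 − 1, about 3.5%. Including the term therefore costs about 1% if centres do not differ, is about neutral at 0.3 SD and gains about 2 to 3% at 0.6 SD. If two added centres differ by 0.6 SD in opposite directions, with assumed sizes 50/30/30, the between-centre variance is (60/110) × 0.36 = 0.196. Then 1.009/√1.196 = 0.92, about 8% narrower.

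**7. Error rate and power.** Change scores were simulated with sizes 70/20/20 and 50/30/30, 4,000 runs per setting (Monte Carlo SE about 0.003 at 5%). The effect was set at 0.70 change SD, where this test has about 95% power (0.70/0.191 = 3.67 = √13.475).

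| Gap in change of added centres | Power without centre | Power with centre |
|---|---|---|
| 0 | 0.95 | 0.95 |
| 0.5 SD | 0.94 | 0.95 |
| 1.0 SD | 0.90 | 0.95 |

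Type I error was 0.046 to 0.056 throughout, with or without the term.

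**The case against.** The strongest reply is that nothing here is an error. No stratification factor is stated, so the model has no design factor to reflect, and a comparison of randomised arms without centre is valid. This stands. Three further points also stand:

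- **Level against change.** Baseline is one of the time points, so stable centre differences in ISI cancel in the time-by-condition contrast (exactly so with complete data).
- **A thin mechanism.** The programme runs on one online platform (section 4) and questionnaires are completed online (section 3). That leaves mainly usual care and case mix. Section 4.1 places usual care with the doctor rather than the centre, and section 5 describes the referrers as neurologists specialised in somnology. A centre term captures doctor and calendar period only in part.
- **Silence.** Section 9.2 is brief and may not list every model term, and some pages were not available for review.

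A reader might infer that a chance centre imbalance goes uncorrected, or that it could move the result by 13 to 32% of the planned d = 0.35 (0.045/0.35 to 0.11/0.35). The documents do not support that reading. The standard error already covers such imbalance, those percentages are 95% limits, and they rest on centre gaps that the plan does not supply.

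What remains is that a multicentre plan silent on centre leaves the adjustment open to a post hoc choice, when settling it in advance costs almost nothing.

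**Conclusion.** The point holds as a cheap improvement of low severity. The planned test is unbiased over randomisations and keeps its error rate. Under assumed gaps of 0.3 to 0.6 SD in ISI change, with the added centres differing in the same direction, leaving centre out widens the 95% interval by about 0 to 4%. A visible loss of power, to about 0.90, needs a 1.0 SD gap, which is beyond that range. All sizes depend on assumed centre shares, centre gaps and rho = 0.5.

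Two further inferences should be avoided. The documents do not establish that there are exactly three centres: section 16 adds two to an unstated number, section 1 mentions one university clinic, and section 10.2.1 allows more. Nor do they show that centre is already in the analysis data: it is absent from the baseline items in sections 3.1.2 and 3.2, and section 15 says that only email and code are entered at registration.

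**What to change.** In section 9.2, prespecify centre and centre-by-time as fixed effects in the primary ISI mixed model. The interaction is essential, because a centre main effect alone would not address differences in change. Use one level per enrolling centre, taken from the enrolment documentation that centres keep under section 10.1, and state in advance how very small centres will be pooled. Leave the randomisation as it is.

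The cost is a sentence or two in the plan, a few degrees of freedom, an interval about 1% wider if centres do not differ in change, and the work of linking centre to the coded analysis data. The sample size does not change.

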9.3. SAFETY DATA ANALYSIS

All adverse events arised during the study will be documented and reported to the local ethics committee. All adverse events will be additionally analyzed. There are no statistical criteria for the study termination. The study has been approved by the local ethics committee of the I.M. Sechenov Moscow Medical University (No. 03-20/19.02.2020) and has been prospectively registered in ClinicalTrials.gov Protocol Registration and Results System (Identifier: NCT04300218 21.04.2020).

10. RESEARCH PLAN

10.1. RESPONSIBILITIES OF RESEARCH CENTRE

- Selection of participants in accordance with inclusion and non-inclusion criteria
- Carrying out the procedure of informed consent form signing
- Timely transferring participants data to the primary investigator (PI) and sub-investigators (SI).
- Providing assistance to participants during baseline online assessment and completion sleep diaries.

-
- Documentation of enrollment of participants, procedure of informed consent form signing, adverse events if any.
 - Timely notice PI of adverse events.

10.2. DEVIATIONS FROM THE RESEARCH PLAN

All deviations from the research plan will be registered and justified. PI is responsible for notifications local ethical committee and the relevant authorities and will be notified about these deviations.

10.2.1. Corrections of the research plan

All corrections of research plan will be agreed with PI, registered and justified. Inclusion of additional clinical centres, SIs and research methods will be agreed with the PI and the local ethical committee. The deviations from the research plan will be analyzed in order to make a decision about possible corrections of the research plan or termination of the research.

10.3. ADVERSE EVENTS AND UNDESIRABLE EFFECTS OF THE INVESTIGATED METHOD

The local ethical committee will be timely notified about serious adverse events and serious undesirable effects of the investigated iCBT-I course.

10.4. EARLY STUDY TERMINATION OR SUSPENSION

The PI, local ethical committee or relevant authority is authorized to preliminarily terminate the study or suspend it in a particular clinical centre or in all clinical centres for significant and documented reasons. If an unacceptable risk for participants is suspected during the clinical study or serious and/or multiple deviations are revealed or if it is mandated by the local ethical committee the PI should suspend the study until its risks will be reevaluated. In case of an early study termination or suspension the PI should timely notify all participating entities and SIs. In case of an early study termination further monitoring of participants is not provided.

11. POSSIBILITY OF PUBLISHING THE RESULTS OF STUDY

Coded personal data of the participants (without specifying the last name, first name and other personal data) derived from Qualtrics and Sleepsy can be used for further statistical analysis and publication of results. The study has been registered in ClinicalTrials.gov Protocol Registration and Results System (Identifier: NCT04300218 21.04.2020). and the protocol of the study was published in a peer-reviewed journal. Results of this trial will be disseminated via peer-reviewed journal publications. Primary and secondary aims will be reported in a single publication. Other findings will be published separately. The results of this study will also be available on the ClinicalTrials.gov website when they become available.

12. INFORMED CONSENT FORM (ICF)

Informed consent is obtained during the procedure of the informed consent form signing with the personal signature and date. The informed consent form prepared in conformity with requirements Rules of Good Clinical Practice of the Eurasian Economic Union approved by Decision of the Eurasian Economic Commission No. 79 dated 3 November 2016. Participants of the study also sign the consent to process personal data, prepared in conformity with Federal Law dated 27 July 2006 N 152-FL (ed. dated 31 December 2017) "On Personal Data".

13. WORK WITH DATA AND DOCUMENTATION.

Personal data of participants of the study obtained at online platform Qualtrics are coded. Participants enter their name and surname solely during the procedure of informed consent form signing. Further communication with them is carried out through the emails. Access to the identification codes of participants will be password secured. Signed informed consent forms will be stored in the PI office. The data retention period is 10 years after completion of the study.

14. FUNDING AND INSURANCE

Work on the protocol is supported by ESKAS Swiss Government Excellence scholarship 2019-2020

15. PRIVACY

Personal data of participants of the study obtained at online platform Qualtrics are stored in depersonalized form. When a new participant is registered in the system only their email and identification code are entered. Identification of a participant is possible when matching individual code with email in Qualtrics and email with name and surname in the ICF. Access to the identification codes of participants in Qualtrics will be password secured; signed informed consent forms will be stored in the PI office. Data collected within iCBT-I program (Sleepsy) will be stored on the password secured server. Privacy of the participants of the study will be protected by existing laws and regulations of Russian Federation. All the data of study participants obtained from medical records will be treated as confidential information. Participants have a right to have access to information on their state of health. Name, surname and other uncoded personal data will not be published in the study reports and publications.

16. TIMEFRAMES OF THE STUDY

- Study approval at a Chair of neurology of Sechenov University meeting 26.11.2019
- Study approval by local ethical committee – February 2020
- Experimental part of the study – February 2020 – December 2021:

-
- Start of data collection – February 2020;
 - Inclusion of two additional clinical centres - February 2021;
 - Completion of data collection - December 2021;
 - Statistical analysis, publication of results – January-February 2022

17. COMPLIANCE WITH THE REQUIREMENTS OF CURRENT LEGISLATION

Study protocol is elaborated in accordance:

- GOST R ISO 14155-2014 Clinical investigation of medical devices for human subjects – Good clinical practice (ISO 14155:2011, IDT) dated - 2015-06-01
- Essential Principles - Global Harmonization Task Force, 1999
- Federal Law «on personal data» dated 27 July 2006 № 152-FL;
- Order of Ministry of Public Health of RF dated 1 April 2016 № 200н «On Establishing the Rules for Good Clinical Practice »;
- Rules of Good Clinical Practice of the Eurasian Economic Union approved by Decision of the Eurasian Economic Commission No. 79 dated 3 November 2016
 - GOST R 52379-2005 «Good clinical practice», approved with the order Federal Agency for Technical Regulation and Metrology dated 27 September 2005 № 232-ст;
 - Resolution of the State Commission for Academic Degrees and Titles Высшей аттестационной комиссии « On the biomedical research in humans», published in the State commission newsletter (2002, № 3);

